6. Participant has been on a stable dose of ACEI and/or ARB therapy for at least 12 weeks prior to screening that is:
 - a. The participant's maximum tolerated dose (MTD), and
 - b. at least one half of the maximum labeled dose (MLD) (See [Section 10.2](#) for minimum ACEI/ARB daily dose requirements at screening).
7. The participant has been on a stable dose of an SGLT2 inhibitor for at least 12 weeks prior to screening.
8. Participant systolic BP must be ≤ 160 mmHg, and diastolic BP must be ≤ 110 mmHg at screening.
9. For participants receiving chronic low dose systemic corticosteroids (defined as ≤ 10 mg/day prednisone or equivalent), or an enteric formulation of budesonide and/or a mineralocorticoid receptor antagonist (MRA), the dosage must be stable for ≥ 12 weeks prior to screening.
10. The participant is willing to undergo a change in ACEI and/or ARB and anti hypertensive medications.

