### **6.5.2. Standard Calculations**

Variables requiring calculation will be derived using the following formulas:

- Days – A duration expressed in days between 1 date (*date 1*) and another later date (*date 2*) will be calculated using the following formulas:  
$$\text{duration in days} = \text{date2} - \text{date1} + 1$$
- Weeks – A duration expressed in weeks is calculated as the number of days divided by 7
- Months – A duration expressed in months is calculated as the number of days divided by 365.25/12 (approximately 30.4)
- Years – A duration expressed in years is calculated as the number of days divided by 365.25
- Height – Height entries made in inches (in) are converted to centimeters (cm) using the following formula:  
$$\text{height (cm)} = \text{height (in)} \times 2.54$$

- Weight – Weight entries made in pounds (lb) are converted to kilograms (kg) using the following formula:  
weight (kg) = weight (lb) / 2.2046
- Temperature – Temperature entries in degrees Fahrenheit are converted to degrees Celsius using the following formula:  
temperature (degrees Celsius) = 5 / 9 × (temp [degrees Fahrenheit] – 32)
- Change from baseline – Change from baseline will be calculated as:  
Change = post baseline value – baseline value
- Percent change from baseline – Percent change from baseline will be calculated as:  
Percent change = ([post baseline value – baseline value]/baseline value) × 100

For variables requiring log transformation, natural log will be used.

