## **6.6.3. Missing Adverse Event or Concomitant Medication Onset Date**

AEs and concomitant medications with incomplete onset dates will be assumed to have started during the study in accordance with the following prioritized list of assumptions:

1. Missing year: event or medication assumed to have the same year as first dose of study medication or year of end date, whichever is earlier.
2. Missing month: event or medication assumed to have started during the study if the year is the same or later than the year of the first dose of study medication. Event or medication assumed to have started at the same month of the first dose of study medication or same month as end date (if year of end date  $\leq$  year of event), whichever is earlier.
3. Missing day: event or medication assumed to have the same day as first dose of study medication if the year and month of onset are the same as year and month of first dose of study medication or the same day as end date, whichever is earlier. Otherwise, the day is assumed to be the first of the month.

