### 7.3. Protocol Deviations

Protocol deviations for missed visits, missed assessments, out-of-window visits or assessments, and violations of inclusion/exclusion criteria (where possible) will be determined based on available data. The clinical research associates will collect all other protocol deviations. Protocol deviations will be classified as critical, important, major, or minor as follows:

- Critical: A deviation from Protocol-related procedures that threatens integrity of data, adversely affects subjects and/or could invalidate acceptability of a project (or part of it). Such deviations require immediate action. This classification will only be used for a confirmed Serious Breach or a serious quality issue. Both circumstances will involve Quality Assurance.
- Important: A subset of protocol deviations that may significantly impact the completeness, accuracy and/or reliability of key study data or that may significantly affect a subject's rights, safety or well-being.

- Major: A deviation from Protocol-related procedures that could affect integrity of the data or adversely affect subjects. Such deviations require timely action.
- Minor: A deviation from accepted procedures that will not adversely affect subjects or data integrity but should be dealt with appropriately.

Protocol deviations that could potentially affect the efficacy or safety conclusions of the study will be identified, and the assessment of determination of evaluable patients for the PPAS will be performed and approved by the Study Statistician, Medical Monitor and Clinical Study Manager prior to database lock.

Evaluability of patients will be based on the following:

- Compliance of study entry criteria (inclusion and exclusion)
- Adequate study medication exposure (no extended dosing interruptions)
- Adequate treatment compliance based on prescribed dose level (within 80% to 120%)
- No prohibited concomitant medications or therapies during the study
- No other major protocol deviations that may affect efficacy or safety conclusions, including the following:
  - Non-withdrawal although at least 1 withdrawal criterion was met.
  - Extensive visit window violations
  - Extensive missing visits
  - Nonadherence to study procedures
  - Inadequate handling of study medication

Critical/Important/Major protocol deviations will be summarized by deviation category and presented in a by-patient data listing.

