## 7.5. Baseline IgAN Disease Characteristics

Baseline IgAN disease characteristics will be summarized using data collected from the IgAN History eCRFs. The following variables will be summarized:

- Age at IgAN diagnosis

- Years since renal biopsy to time of informed consent
- Time in weeks on SGLT2 inhibitor prior to enrollment (start of sparsentan treatment) is calculated as defined in [Section 6.5.2](#)

Baseline IgAN disease characteristics will be summarized and presented for both the FAS and PPAS. A by-patient listing will also be provided.

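### The SAP's partial-date rule can date an established SGLT2 inhibitor to the first sparsentan dose, a start that eligibility rules out; total SGLT2 inhibitor duration is then understated and the drug is tabulated as new

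*SAP*

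**What the plan says.** SAP 6.6.3 states its scope at the start: "AEs and concomitant medications with incomplete onset dates will be assumed to have started during the study". Three steps follow.

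- Year missing: "event or medication assumed to have the same year as first dose of study medication or year of end date, whichever is earlier".
- Month missing: "Event or medication assumed to have started at the same month of the first dose of study medication", or the end-date month if that is earlier.
- Day missing: "event or medication assumed to have the same day as first dose of study medication if the year and month of onset are the same" (the comparison is with the first dose), or the end-date day if earlier. In any other month the day is set to the first.

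No exception is made for drugs that must predate the study.

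Protocol 5.1, criterion 7, requires this: "The participant has been on a stable dose of an SGLT2 inhibitor for at least 12 weeks prior to screening". Criterion 9 sets the same 12-week stability requirement for low-dose systemic corticosteroid, enteric budesonide and mineralocorticoid receptor antagonist (MRA) in participants who take them. The Schedule of Activities places screening between Day -42 and Day -1.

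The SGLT2 inhibitor start date, or the dates of concomitant medications generally, feed three outputs: total SGLT2 inhibitor duration (SAP 9.3), the split between prior and new concomitant medications (SAP 9.4), and time on the drug before sparsentan began (SAP 7.5, drawn from the IgAN History eCRFs).

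**The concern.** Assuming that an undated event began on study is a cautious default for adverse events. For a background drug it contradicts what eligibility has already established. The safety objective concerns sparsentan added to chronic, stable SGLT2 inhibition, and the SGLT2 inhibitor duration and medication tables are where a reader checks that this was the population studied. One affected record is enough to put an impossible minimum in the total-duration row and to list long-standing therapy as started on treatment. Background corticosteroid, budesonide or MRA with the same gap in its start date would be misclassified in the same way.

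**Working it through.** There is no sponsor figure to reproduce here; the check applies the rule as written.

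**Inputs**

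- Minimum use before screening: 12 weeks = 84 days (criterion 7).
- Screening to Day 1: 1 to 42 days (Schedule of Activities).
- Week 28 target: Day 197 (SAP Table 1).
- Duration convention: date2 − date1 + 1 days, and "A duration expressed in weeks is calculated as the number of days divided by 7" (SAP 6.5.2).

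**Step 1. What the rule returns.** Take an ongoing drug and a first dose on 2 Oct 2023.

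| Recorded start | Start under SAP 6.6.3 |
|---|---|
| 2023 only | 2 Oct 2023 (first dose) |
| Nothing recorded | 2 Oct 2023 (first dose) |
| 10 Mar, year missing | 10 Mar 2023 (right if the true year is 2023) |
| 10 Nov, year missing | 10 Nov 2023 (after the first dose) |
| 2022 only | 1 Oct 2022 |

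The rule was also run over a grid of first-dose dates and true starts at least 84 days before screening. The first two patterns gave the first-dose date every time and were never correct. When the month is missing in the first-dose year but the day is known, the date falls in the first-dose month, usually not on the first-dose day. It was again never correct, with an error of about 60 days or more.

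**Step 2. Smallest possible error for the first two patterns.** The latest start that eligibility allows is 84 + 1 = 85 days before Day 1 (screening on Day -1), or 84 + 42 = 126 days (screening on Day -42).

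**Step 3. Total duration to Week 28 (SAP 9.3), drug still ongoing.**

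- Under the rule: 197/7 = 28.1 weeks.
- Bounded by eligibility: at least (85 + 197)/7 = 40.3 to (126 + 197)/7 = 46.1 weeks.
- Understatement: at least 85/7 = 12.1 to 126/7 = 18.0 weeks, which is 85/282 = 30% to 126/323 = 39%.

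**Step 4. Time before sparsentan (SAP 7.5), if SAP 6.6.3 is applied to it.**

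- Under the rule: 1/7 = 0.14 week.
- Bounded by eligibility: at least (85 + 1)/7 = 12.3 to (126 + 1)/7 = 18.1 weeks.

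**Step 5. Classification (SAP 9.4).** A drug that starts on the date of the first dose is counted as new. The same section also sends starts that cannot be placed because of a partial date to the new category, and it does not say that eligibility confirmation settles the question.

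**Step 6. Concomitant duration (SAP 9.3).** The clock starts on or after the first sparsentan dose, so 24 weeks of joint treatment gives 168/7 = 24.0 weeks with either start date.

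**Step 7. Effect on a mean.** The documents do not give the number of affected records. If 3 to 6 of 60 were affected (an assumption), mean total duration would fall by at least 3 × 12.1/60 = 0.6 to 6 × 12.1/60 = 1.2 weeks.

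**The case against.** The case for leaving the text alone is that very little depends on it. Sites must record start dates and confirm at least 12 weeks of use, so such gaps may be rare. The affected outputs are descriptive rows in a single-arm exploratory study with no efficacy hypothesis. SAP 7.5 takes its data from the IgAN History eCRFs, and SAP 6.6.3 does not say that it governs that form. The general statement in SAP 6.6 is that missing values are not imputed. All of this stands. It limits the size of the point and makes the SAP 7.5 consequence conditional, but it does not make a Day 1 start possible.

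A reader might infer four stronger claims that the documents do not support.

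- **Any missing year leads to the first-dose date.** The first step fills only the year. A known month and day are kept, and the result can be exactly right.
- **Every SGLT2 inhibitor duration is wrong.** Duration concomitant with sparsentan is unchanged. The impossibility also holds only for an eligible participant's initial record: the Full Analysis Set can include eligibility violators, restarts can truly begin on study, and an earlier end date moves the imputed start.
- **Participants would be dropped from the Per Protocol set.** SAP 7.3 says that "violations of inclusion/exclusion criteria (where possible) will be determined based on available data". It does not mention imputed dates, and the Study Statistician, Medical Monitor and Clinical Study Manager approve evaluability before database lock. A false flag is conceivable, but no such procedure is described.
- **A re-dated background steroid would alter the primary result.** SAP 8.1 defines on-treatment values by sparsentan dosing alone, so a steroid start date removes no UA/C value. The listed intercurrent event is also limited to renal indications.

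**Conclusion.** The point holds, and it is minor. For an ongoing SGLT2 inhibitor with month and day missing in the first-dose year, or with no start date at all, SAP 6.6.3 as written gives a start that criterion 7 excludes for an eligible participant's initial record. Each such record loses at least 12.1 to 18.0 weeks of total duration and is listed as a new concomitant medication. The loss of prior time under SAP 7.5 depends on whether the rule is used there, which the SAP leaves open. Drugs covered by criterion 9 share the classification error. No UA/C estimate or adverse event incidence changes. The bounds assume that eligibility was met, that the drug was still ongoing at a Week 28 visit on its target day, and that screening took place 1 to 42 days before Day 1.

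**What to change.** Amend SAP 6.6.3 and 9.4 as follows.

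- Exempt the SGLT2 inhibitor, and any other background drug whose use for at least 12 weeks before screening was confirmed at eligibility, from the on-study start assumption.
- Impute an incomplete start as the latest date that agrees with the recorded parts and is at least 84 days before screening. Report the resulting duration as a lower bound. If no such date exists, query the record.
- Class these drugs as prior concomitant.
- State that the same rule governs the SAP 7.5 variable.
- Do not use imputed start dates to decide entry-criteria deviations.

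Example: recorded start 2023 only, first dose 2 Oct 2023, screening 42 days earlier on 21 Aug 2023. Counting back 84 days gives 29 May 2023. Prior time is then (126 + 1)/7 = 18.1 weeks, shown as a lower bound.

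The cost is a few sentences and a small programming exception. It needs no new data beyond the occasional query.

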## **6.6.4. Missing Adverse Event or Concomitant Medication End Date**

If the entire end date is unknown and the event or concomitant medication is not considered ongoing at the end of study or follow-up, the event or medication will be assumed to have ended on the last date of contact for the patient.

If only the day of end date is unknown, the day will be assumed to be the last of the month or the last date of contact for the patient, whichever is earlier.

If both the day and month of end date are unknown, the event or medication will be assumed to have ended on the last day of the year or the last date of contact for the patient, whichever is earlier.

## **6.6.5. Missing Adverse Event Severity or Relationship**

An event with missing severity will be considered severe. An event with missing relationship will be considered related to study medication and SGLT2 inhibitor.

## 7. STUDY POPULATION

### 7.1. Patient Disposition

Patient disposition will be tabulated and will include the number of patients who screened, failed screening, enrolled, received study medication, completed study medication, discontinued study medication (including reasons), completed the study, and discontinued the study (including reasons). Percentages will be calculated out of the number of patients enrolled. Percentages will not be displayed for the number of patients screened or the number of patients who failed screening.

The number and percentage of patients in each analysis set will be summarized.

Patient enrollment by study site and country will be tabulated by treatment group.

A by-patient listing of inclusion into the analysis sets and study medication/study completion information including reason for study medication discontinuation or early withdrawal from study, if applicable, will be presented.

A Kaplan-Meier plot of time to study termination or early withdrawal will be presented. Patients who withdrawal early from study will be considered an event at the time (weeks) of study withdrawal. Patients who do not discontinue will be censored at the time (weeks) of study completion as follows:

Weeks until completion = (date of completion - date of treatment initiation + 1)/7.

Weeks until early withdrawal = (date of early withdrawal - date of treatment initiation + 1)/7.

Similarly, a plot of time to treatment discontinuation will be presented. Patients with treatment for at least 162 days will be considered to have completed treatment.

### 7.2. Screen Failures

The reason for screen failures will be summarized by site, as appropriate.

### 7.3. Protocol Deviations

Protocol deviations for missed visits, missed assessments, out-of-window visits or assessments, and violations of inclusion/exclusion criteria (where possible) will be determined based on available data. The clinical research associates will collect all other protocol deviations. Protocol deviations will be classified as critical, important, major, or minor as follows:

- Critical: A deviation from Protocol-related procedures that threatens integrity of data, adversely affects subjects and/or could invalidate acceptability of a project (or part of it). Such deviations require immediate action. This classification will only be used for a confirmed Serious Breach or a serious quality issue. Both circumstances will involve Quality Assurance.
- Important: A subset of protocol deviations that may significantly impact the completeness, accuracy and/or reliability of key study data or that may significantly affect a subject's rights, safety or well-being.

- Major: A deviation from Protocol-related procedures that could affect integrity of the data or adversely affect subjects. Such deviations require timely action.
- Minor: A deviation from accepted procedures that will not adversely affect subjects or data integrity but should be dealt with appropriately.

Protocol deviations that could potentially affect the efficacy or safety conclusions of the study will be identified, and the assessment of determination of evaluable patients for the PPAS will be performed and approved by the Study Statistician, Medical Monitor and Clinical Study Manager prior to database lock.

Evaluability of patients will be based on the following:

- Compliance of study entry criteria (inclusion and exclusion)
- Adequate study medication exposure (no extended dosing interruptions)
- Adequate treatment compliance based on prescribed dose level (within 80% to 120%)
- No prohibited concomitant medications or therapies during the study
- No other major protocol deviations that may affect efficacy or safety conclusions, including the following:
  - Non-withdrawal although at least 1 withdrawal criterion was met.
  - Extensive visit window violations
  - Extensive missing visits
  - Nonadherence to study procedures
  - Inadequate handling of study medication

Critical/Important/Major protocol deviations will be summarized by deviation category and presented in a by-patient data listing.

## 7.4. Demographic and Baseline Characteristics

Demographic variables will include the following:

- Age (at informed consent)
- Sex
- Race
- Ethnicity

Other baseline characteristics will include the following:

- Weight (kg)
- Height (cm)
- Body mass index (kg/m^2)
- BP (systolic and diastolic)
- Childbearing potential (for females only)

- Hemoglobin A1c (%)
- Blood glucose (mmol/L)
- Glycosuria (Urine glucose values of “Trace”, ‘1+’, ‘2+’, ‘3+’, ‘Present’, etc)
- Hematuria (Urine Blood/Hgb values of “Trace”, ‘1+’, ‘2+’, ‘3+’, ‘Present’, etc)
- UA/C
- eGFR (mL/min/1.73 m^2), continuously and including the following categories:
  - <25 mL/min/1.73 m^2, ≥25 to <60 mL/min/1.73 m^2, ≥60 mL/min/1.73 m^2
  - <15 mL/min/1.73 m^2, ≥15 to <30 mL/min/1.73 m^2, ≥30 to <45 mL/min/1.73 m^2, ≥45 to <60 mL/min/1.73 m^2, ≥60 to <90 mL/min/1.73 m^2, ≥90 mL/min/1.73 m^2
- UP/C (g/g), continuously and including the following category.
  - ≤1.25 g/g, >1.25 g/g
- Current RAASi at Screening and at Day -1
  - Any RAASi
  - RAASi at maximum labeled dose (MLD)
  - ACEI at MLD
  - ARB at MLD
  - ACEI and ARB at MLD
  - ACEI or ARB at MLD
- Baseline concomitant medication use\*
  - Antihypertensive medications, lipid-lowering medications, Immunosuppressive agents with renal indication (ie, steroids, calcineurin inhibitors, mycophenolate mofetil and other immunosuppressive agents). Renal indication will be determined via medical review of concomitant medications and associated indications.

\* Medication lists will be reviewed and documented prior to the database lock to finalize the list of medications to be included in each category.

Demographics and baseline characteristics will be summarized and presented for both the FAS and PPAS. All baseline characteristics will use the last available data prior first dose of study medication except UA/C and UP/C will use the definition described in [Section 6.4.2](#). A by-patient listing will also be provided.

## 7.5. Baseline IgAN Disease Characteristics

Baseline IgAN disease characteristics will be summarized using data collected from the IgAN History eCRFs. The following variables will be summarized:

- Age at IgAN diagnosis

- Years since renal biopsy to time of informed consent
- Time in weeks on SGLT2 inhibitor prior to enrollment (start of sparsentan treatment) is calculated as defined in [Section 6.5.2](#)

Baseline IgAN disease characteristics will be summarized and presented for both the FAS and PPAS. A by-patient listing will also be provided.

## 7.6. Medical History

Verbatim terms on eCRFs will be mapped to preferred terms (PTs) and system organ classes (SOCs) using Medical Dictionary for Regulatory Activities Terminology (MedDRA).

Medical history will be summarized by SOC and PT using the FAS. Summaries will be ordered by descending order of incidence of SOC and PT within each SOC. A by-patient listing will also be provided.

## 8. EFFICACY

### 8.1. General Considerations

All efficacy analyses will be done descriptively on the FAS using observed data only. Change from baseline (or percent change from baseline, as appropriate) will be summarized with mean and 95% CI, as appropriate. For categorical efficacy endpoints, the proportion of participants in the category will be presented along with corresponding 95% CI.

The primary and secondary efficacy endpoint analyses based on the PPAS will be performed as sensitivity analyses. All primary efficacy analyses based on laboratory data will use central laboratory data only.

Albuminuria (UA/C) and proteinuria (UP/C) will be determined based on a FMV samples. As UA/C and UP/C are highly right-skewed variables, analyses will be performed on log-transformed data. For ease of interpretation, results will be presented in the original units.

The eGFR for each baseline and post-baseline visit will be determined using the Chronic Kidney Disease Epidemiology Collaboration ([Levey 2009](#)) formula for adults based on serum creatinine values from the visit.

For the purposes of efficacy analyses, an assessment is considered “on treatment” if it occurs after the first dose of study medication and no more than 3 days after last dose of study medication for the patient. Additionally, efficacy analyses may be repeated using all on-study data.

